centers in the U.S. The laboratory uses published methods and reports results with a clinically useful interpretation (70-72). Other laboratories can be used if equivalent results can be obtained. Although results from different laboratories are likely to be comparable, this has not been verified. Normal ranges are likely to be less comparable between laboratories than elevated abnormal values. It is desirable to use the same laboratory for porphyrin testing throughout the study. In general, Quest, LabCorp, ARUP or Mayo are suitable for urine and plasma porphyrin measurements. However plasma porphyrin fluorescence peak testing is only done at UTMB and ARUP. The treatment outcomes are based on criteria stated in this protocol rather than on normal ranges stated by different laboratories, which may vary considerably.

Molecular analyses to identify *UROD* mutations are provided by the Genetic Testing Laboratory at the Icahn School of Medicine at Mount Sinai in New York City.

4.B. Design. This is an open-label comparative study of the two standard treatments for PCT. Participants will be assigned to the treatment for which they are eligible, as determined by strict medical criteria as outlined in this protocol. Participants eligible and willing to receive either treatment will be randomized across sites; however the majority of participants are expected to be assigned a treatment based on their medical indications and preference. Based on many decades of clinical experience, both treatments are accepted as effective and safe. Therefore, comparing efficacy and safety will not be an objective of these standard of care treatments. Rather, the main objectives will be to compare time needed to achieve remission, as assessed by documented primary and secondary biochemical and clinical outcomes, and the durability (i.e. lack of disease recurrence) after each treatment. Since phlebotomy and low dose hydroxychloroquine are both considered accepted alternatives for treatment of PCT, costs will be either considered standard of care and charged to insurance or supported by the Porphyrias Consortium grant for those participants without insurance.

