4.D. Recruitment and availability. Participants with PCT will be obtained primarily by referral to the participating centers. Physicians in primary care and specialty clinics such as dermatology and gastroenterology are made aware through personal contacts and notices of this treatment study and asked to refer participants. Notices are also sent to primary physicians and specialists in the referral area for each center in order to attract additional participants. We anticipate enrolling ~60 additional participants over the second 5-year cycle of funding of the Porphyrias Consortium to bring the total enrollment to at least 100. Thus the total target enrollment period will be 10 years.

Feasibility of recruitment is based on data from UTMB, which has been studying PCT and capturing all patients seen at that institution for many years. On average, we expect to enroll 8-10 patients with new onset or recurrent PCT per year at UTMB. Over the second 5-year period of Porphyrias Consortium funding we can expect to enroll a total of 40-50 patients at UTMB. With contribution from the other 6 centers, we expect to achieve the recruitment objective of ~60 new patients.

4.E. Enrollment and treatment assignment. Subjects will be enrolled if they meet the inclusion and exclusion criteria shown in Table 1, which should allow inclusion of the great majority of individuals who present with PCT. PCT patients are often unsponsored, and may be unable to afford either of the standard treatments in this study or to attend scheduled study visits. To assure both study adherence and optimal management, treatment and study costs will be covered either by participants' insurance or other funding if the participant does not have insurance, at the discretion of the study site. Reimbursement for travel and time lost for study participation will be at the discretion of each study site. This will help to enable all who need therapy for PCT to be treated within the study.

A history and physical examination will be carried out, which will help document the diagnosis and identify susceptibility factors such as alcohol and estrogen use and smoking, which will then be assessed in more detail by alcohol and smoking questionnaires. The results of the history, physical examination and screening laboratory tests will be recorded on Case Report Forms (CRFs) prepared for this study.

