- 1. Evidence for another cause of blistering skin lesions, such as another type of cutaneous porphyria, or pseudoporphyria
- 2. Pregnancy
- 3. Prior treatment by phlebotomy, hydroxychloroquine or chloroquine within one month, unless all appropriate lab results from before treatment was started can be obtained, to document baseline porphyrin levels.
- 4. Unwillingness to comply with the protocol and required visits
- 5. Previous treatment as a participant in this protocol.

Pregnant women will not be included in the study, because it is generally recommended that treatment of PCT be delayed in pregnant women until 1-2 months after delivery. Phlebotomies may induce borderline iron status during pregnancy, which may compromise fetal health. Usage of 4-aminoquinoline compounds during pregnancy should be avoided because these drugs cross the placenta and accumulate in ocular tissues of the fetus.

In very rare instances a subject that is an excellent candidate for the study may not meet all inclusion/exclusion criteria. If the investigator feels the subject may still be a good candidate for the study, entrance to the study will be reviewed with the Study Chair and the site's IRB to determine participation. Reasons for the exception must be recorded on the CRF. The objective is to include in the study all patients who need to be treated and obtain information and experience to better define future treatment guidelines.

Documentation of PCT will include consistent cutaneous symptoms and signs, increases in urinary total porphyrins with a predominance of highly carboxylated porphyrins (uroporphyrin, hepta-, hexa- and pentacarboxylate porphyrin) and increased plasma total porphyrin with a plasma fluorescence emission spectrum at neutral pH at 619~620, which is consistent with PCT. Participants with subclinical PCT (i.e. without skin manifestations) and biochemical documentation can also be included. Additional testing will exclude other blistering cutaneous porphyrias such as variegate porphyria, and erythrocyte total porphyrin measurement will exclude congenital erythropoietic porphyria, which rarely mimics PCT. Samples required for these tests prior to treatment include a 24 hour urine collection or a spot urine sample, a blood sample; a random fecal sample is optional but recommended. Testing and laboratory methods will include the following:

- Plasma total porphyrins (25, 26, 64)
- Urinary δ-aminolevulinic acid and porphobilinogen (73)

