Liver ultrasound and biopsy will be recommended to participants based on clinical indications per the investigator, these tests will not be done solely for the study. If completed at an outside institution records will be obtained. Tissue will be examined microscopically, and iron content will be measured if possible. Evaluation of liver histology is not required for this study because the results are usually not essential for diagnosis or classification of PCT participants, identifying risk factors, or deciding on treatment options. However, liver biopsy is the best means of assessing liver iron concentration, and is often recommended for assessing the degree of pretreatment damage to the liver associated with hepatitis C, alcohol, steatosis, etc. Results of liver biopsy, when available, will be recorded on the CRFs and tabulated and analyzed with other clinical information that pertains to PCT.

Treatment assignment. Before assigning treatment, subjects will be evaluated for the contraindications to treatment with hydroxychloroquine and phlebotomy listed in Table 3 and 4.

If one of these treatments is contraindicated, the reason(s) will be recorded, and the subject will be assigned to the other treatment. Participants eligible for both will be assigned by randomization.

Table 3. Contraindications to treatment with hydroxychloroquine.

- 1. Unwillingness to consider this form of treatment
- 2. Lactating women
- 3. Psoriasis
- 4. Significant retinal disease
- 5. Glucose-6-phosphate dehydrogenase deficiency
- Recent and continued heavy use of alcohol (defined as 28 or more drinks per week)
- 7. Recent and continued use of hepatotoxic drugs such as acetaminophen, isoniazid or valproic acid
- Marked abnormalities in liver function tests at baseline, such as serum bilirubin >3mg/dL, serum alanine aminotransferase >200 U/L, or prothrombin time >16 seconds (or INR >1.4)
- 9. Advanced renal disease, with serum creatinine >3 mg/dL
- 10. Poor tolerance or poor response to this treatment in the past
- 11. HFE genotypes C282Y/C282Y or C282Y/H63D and serum ferritin above the normal range (>336 ng/mL)
- 12. Substantial iron overload, with serum ferritin >500 ng/mL, in the absence of these *HFE* genotypes
- 13. Marked iron overload (3+ or 4+) on liver biopsy, if available

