Continued heavy use of alcohol is unusual in most PCT participants. Most were moderate rather than heavy drinkers, and in our experience most discontinue or greatly reduce their intake of alcohol when so advised during the study. Therefore, we seldom need to exclude hydroxychloroquine treatment in PCT because of heavy use of alcohol. Most participants also smoke cigarettes, and are less successful in reducing or stopping this addiction.

Participants with serum ferritin concentrations >500 ng/mL or with marked iron overload on liver biopsy will not be considered for treatment with hydroxychloroquine, since they will be considered clinically to likely have substantial iron overload and require treatment by phlebotomy. Participants with the *C282Y/C282Y or C282Y/H63D HFE* genotypes often have serum ferritin concentrations in the normal range, do not have iron overload and will be eligible for either treatment. Those with these genotypes and ferritins >336 ng/mL (the upper limit of normal) will not be randomized, since we consider that phlebotomy is indicated with these genotypes when iron overload is evidenced by a high ferritin level, and PCT participants with the *C282Y/C282Y* genotype and high ferritin are reported to be resistant to low dose 4-aminoquinolines (48).

Table 4. Contraindications to treatment with phlebotomy.

- Unwilling to consider this form of therapy
- 2. Severe bone marrow dysfunction manifested by anemia
- 3. Poor venous access
- 4. Poor tolerance in the past, such as frequent syncopal episodes, or poor response

Most participants with HIV infection and PCT will be eligible for either treatment. HIV participants with PCT generally tolerate phlebotomy and can be assigned to this treatment

unless there is evidence of bone marrow failure, in which case they would be eligible for treatment with low-dose hydroxychloroquine.

Participants with chronic hepatitis C (HCV) and PCT will be eligible for either treatment. Prospective participants will be evaluated for inclusion in PC7210 for HCV treatment first. If they are not eligible or decline participation in PC7210, they will be offered enrollment in PC7206, Patients who are eligible for PC7210 will include PCT patients >18 years old with HCV genotype 1. Major exclusion criteria for this study include patients who are currently receiving PCT treatment by phlebotomy or hydroxychloroquine, alcohol abuse, amiodarone use, other comorbid conditions.

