The study will continue as a more pragmatic study relevant to clinical practice, with assignment to treatment based on uniform criteria and randomization only of participants eligible for both treatments, to avoid unnecessary bias. Therefore, it will be a two-group study with no substudy. A descriptive approach to data analysis will be employed, with clinically relevant comparisons of the two treatments, rather than a noninferiority analysis.

Inclusion of all available participants rather than just the minority that can be randomized has a number of advantages. Participants eligible for both treatments (and therefore eligible for randomization) might respond differently than those who are not, since some of the reasons that make participants ineligible for one treatment relate to certain susceptibility factors and to prior treatment experience. Exclusion of a majority of participants from treatment comparisons also would make the study less pragmatic and less clinically relevant. In the interim analysis, randomized and nonrandomized participants did not differ in terms of clinical and demographic

features, but such important comparisons would be more meaningful with a larger number of participants. In the amended study, participants who are eligible for both treatments are to be randomized as a method for choosing between treatments that is needed in the study to avoid bias, but not as a study design feature. Bias might arise, for example, from existing site-specific treatment preferences.

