The following susceptibility factors for PCT will be summarized and tabulated, and examined for balance across treatment groups. Differences in response based on susceptibility factors will be examined by multivariate analysis. The following susceptibility factors will be emphasized in this analysis:

- 1. Alcohol use (presence or absence)
- 2. Smoking (presence or absence)
- 3. Estrogen use (presence or absence)
- 4. Hepatitis C (presence or absence)
- 5. HIV (presence or absence)
- 6. UROD mutations (presence or absence)
- 7. HFE mutations (presence or absence of C282Y and H63D, and specific genotype combinations)

The analysis regarding susceptibility factors will take into consideration that some (e.g. homozygotes for HFE mutations with high ferritin levels) are medical reasons for assignment to one treatment group and not the other. We recognize that because the number of participants in subgroups based on susceptibility factors or combinations of susceptibility factors will be

relatively small, and it may not be possible to detect or exclude statistically significant differences for all susceptibility factors. The data is expected to support continuing this study with larger numbers of participants, or to suggest whether other studies should be designed to clarify the effects of these factors on treatment response and durability.

Additional modeling will assess factors affecting the frequency of recurrence and seasonality effects using logistic regression modeling and log-rank testing, respectively.

Sample Size and Power. A sample size calculation was performed to assess power for a study assessing the effect of factors on time to remission. Extremely common or rare factors are detected with 80% power for 90 subjects (and some dropout) when the hazard ratios are 2.3 (alcohol consumption and UROD deficiency), 2.2 (smoking history), 3.2 (estrogen usage), 2.0 (hepatitis C), and 1.9 (HFE mutations). In summary, this approach for times to remission leads to a sample size of approximately 50 subjects per group. All analyses were conducted in nQuery Advisor Version 5.0 (Janet Elashoff (2002); nQuery Advisor Version 5.0 User's Guide. Los Angeles, CA).

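### Prior PCT treatment can set the arm and may affect response, yet it is not prespecified for the balance table, the remission model or the recurrence model

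*Combined protocol and SAP*

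**What the plan says.** **Who enters.** Section 4.D bases recruitment on a mixed population: "On average, we expect to enroll 8-10 patients with new onset or recurrent PCT per year at UTMB". In Table 1 the only exclusions for earlier treatment are "Prior treatment by phlebotomy, hydroxychloroquine or chloroquine within one month" (waived if pre-treatment laboratory results can be obtained) and earlier treatment as a participant in this protocol. A patient treated elsewhere who has since relapsed is eligible.

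**How the arm is set.** Table 3, item 10 contraindicates hydroxychloroquine for "Poor tolerance or poor response to this treatment in the past". Table 4, item 4 contraindicates phlebotomy for "Poor tolerance in the past, such as frequent syncopal episodes, or poor response". Section 4.E then states: "If one of these treatments is contraindicated, the reason(s) will be recorded, and the subject will be assigned to the other treatment". Patients eligible for both treatments are randomized, but section 4.B says "the majority of participants are expected to be assigned a treatment based on their medical indications and preference".

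**How the data are analysed.** Section 4.R includes everyone who starts treatment. Time to remission is compared with Cox models that study susceptibility factors. Seven factors are listed for the balance table and emphasised in the multivariate analysis: alcohol, smoking, estrogen, hepatitis C, HIV, UROD mutations and HFE mutations. For recurrence the text is "Additional modeling will assess factors affecting the frequency of recurrence", by logistic regression, with no covariates listed. The same section explains why patients ineligible for one treatment might respond differently: "some of the reasons that make participants ineligible for one treatment relate to certain susceptibility factors and to prior treatment experience".

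**The concern.** Section 4.R gives two reasons why patients who cannot be randomized may respond differently: susceptibility factors and prior treatment experience. The first gets a list, a balance check, a place in the multivariate analysis, and an undertaking to allow for factors that dictate assignment (HFE homozygotes with high ferritin is the example). The second gets none of these.

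The plan also treats repeat courses inside the study as different from first courses. Data from treating recurrences are analysed separately from first-treatment data (sections 4.F and 4.Q), and a relapse during follow-up stays out of the primary analysis (section 4.E). A patient whose earlier course and relapse took place outside the study is pooled with new-onset patients, and no reason is given.

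Durability is one of the two main objectives in section 4.B. If previously treated patients relapse more often and are unevenly split between the arms, part of any difference in recurrence reflects who was placed in each arm. A pooled recurrence rate would also describe neither group well. The same mechanism could affect time to remission.

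**Working it through.** The plan has no figure to reproduce. The sample-size text covers susceptibility factors and time to remission only, with nothing for recurrence or prior history.

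**Step 1: do the passages connect?** Previously treated patients can enter (Table 1, section 4.D). For some of them history fixes the arm (Table 3 item 10, Table 4 item 4, section 4.E). Randomization protects only a minority (section 4.B), who are pooled with the rest (section 4.R), and the current plan states no randomized-only analysis. The history may go with response (section 4.R) and is not a named covariate. Each link is in the text. How many patients are affected is not.

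**Step 2: possible size with the planned logistic model.** From the documents: about 100 patients, and the interim split of 17 phlebotomy to 13 hydroxychloroquine, so 13/30 = 43% and 17/30 = 57%, or 43 and 57 patients. Assumed: recurrence without prior PCT *b* = 15% or 25%; odds ratio for prior history *OR* = 1.5 to 3; share previously treated *s* = 10–20% on phlebotomy and 20–50% on hydroxychloroquine; no true treatment effect.

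- Recurrence with prior history: *r* = *o*/(1 + *o*), where *o* = *OR* × *b*/(1 − *b*)
- Recurrence in an arm: *s* × *r* + (1 − *s*) × *b*
- Spurious odds ratio: the ratio of the two arms' odds
- False-positive rate: two-sided 5% Wald test on the difference in proportions

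Example: *b* = 0.25 and *OR* = 3 give *o* = 1 and *r* = 0.50. Hydroxychloroquine (*s* = 0.4): 0.4 × 0.50 + 0.6 × 0.25 = 0.350. Phlebotomy (*s* = 0.1): 0.1 × 0.50 + 0.9 × 0.25 = 0.275. Odds ratio: (0.350/0.650)/(0.275/0.725) = 1.42. The standard error is √(0.350 × 0.650/43 + 0.275 × 0.725/57) = 0.094, so the shift is 0.075/0.094 = 0.80 and the false-positive rate is 12.6%.

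| b | OR for history | Share, phlebotomy / HCQ | Spurious OR | False-positive rate |
|---|---|---|---|---|
| 25% | 3 | 20% / 20% | 1.00 | 5.0% |
| 25% | 1.5 | 20% / 30% | 1.04 | 5.1% |
| 25% | 2 | 20% / 40% | 1.16 | 6.2% |
| 25% | 3 | 20% / 50% | 1.40 | 12.3% |
| 25% | 3 | 10% / 40% | 1.42 | 12.6% |
| 15% | 3 | 10% / 40% | 1.45 | 11.2% |

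Swapping the shares inverts the ratio: 1/1.42 = 0.70.

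**Step 3: the same question on a time scale.** Simulation of 1,500 trials per setting, with 50 per arm, 20% five-year recurrence in new-onset patients, 3–5 years of follow-up, no true effect, and a Cox model. Each cell shows two independent runs.

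| Shares previously treated | Hazard multiplier | Unadjusted HR | Type I error |
|---|---|---|---|
| 30% v 20% | 2 | 1.09, 1.07 | 4.7%, 4.5% |
| 40% v 20% | 2 | 1.16, 1.15 | 5.3%, 5.2% |
| 40% v 20% | 3 | 1.26, 1.26 | 8.2%, 7.5% |
| 50% v 20% | 3 | 1.43, 1.41 | 12.5%, 11.7% |

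With equal shares (30% v 30%) the HR was 1.00. The Monte Carlo standard error near 5% is √(0.05 × 0.95/1500) = 0.6 points, so the first two rows show no detectable inflation.

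**Step 4: effect of one yes/no term.** The simulated HR returned to 0.97–1.02 and the error rate to about 4–5.5%. This is built in, since the data were generated from that term. It shows only that a correctly coded term removes bias from this source.

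**Step 5: how many recurrences there would be.** In Step 2 the count runs from about 0.162 × 100 = 16 to 43 × 0.375 + 57 × 0.300 = 33. The Step 3 assumptions give roughly 20–25. If treatment and all seven factors were entered, that is 8 terms, or 2 to 4 recurrences per term.

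**The case against.** **The assignment rules act on poor tolerance or response, not on relapse.** A reader might infer that earlier failure decides the arm for recurrent patients in general. The documents do not support that. A patient who remitted and later relapsed has no contraindication on that ground and, if eligible and willing, is randomized. The Background says relapses are reported to respond to further phlebotomy and calls both treatments almost always effective, and section 4.Q calls failure highly unusual. These are single items among 13 and 4 contraindications, alongside preference and randomization. This stands. It limits the rule-driven part of any imbalance to patients with that specific history, although preference could also differ by history.

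**The plan does not shut prior history out.** A reader might infer that it is deliberately omitted, or that first and repeat relapses are assumed equally likely. Neither is stated. Section 4.R says the seven factors are emphasised, refers to other clinical and demographic features, and leaves the recurrence covariates open. The accurate statement is that prior history is not prespecified. The only other clinical features singled out, in the interim conclusions, are age and sex.

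**Direction and size are unknown.** Poor responders to each treatment move in opposite directions and may cancel. Every input that drives the ratios is assumed, and the mild settings show almost no bias. This stands too.

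**Adjustment has a price.** With so few recurrences, terms for which treatment was given before would strain the model, and for past poor responders the arm is fixed by rule, so such terms rest partly on extrapolation. This argues for a single yes/no term.

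**The analysis is called descriptive and recurrence is a secondary outcome.** That lowers the stakes. But section 4.B still makes durability a main objective, and a descriptive comparison of non-randomized groups needs the relevant history beside it.

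**Conclusion.** The concern holds as a gap in prespecification that is worth closing. The plan pools new-onset and previously treated patients, lets past poor tolerance or response fix the arm for some of them, expects most participants not to be randomized, and accepts that prior treatment experience may go with response. It does not name that history for the balance table, the Cox model or the recurrence model. The remission and durability comparisons are open to confounding.

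A reader might go further and call the durability comparison confounded, or biased against one arm. The documents do not support that, because they give no share of previously treated entrants, no split by arm and no relapse ratio. Under the assumed inputs the spurious ratio is 1.00 with equal shares and about 1.4 (at most 1.45) when large imbalance and a tripled risk coincide, with false-positive rates of about 5% to 13%. It can run the other way. For time to remission the mechanism is the same, but no size was calculated.

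**What to change.** In section 4.R:

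- Define a baseline variable, prior treated PCT (no/yes), taken from the history already needed to apply exclusions 3 and 5 and Tables 3 and 4.
- Add it to the factors tabulated and examined for balance across treatment groups.
- Enter it as a single yes/no covariate in the Cox model for time to remission and in the logistic model for recurrence.
- Tabulate which treatment was given before, and report recurrence for new-onset and previously treated entrants, by treatment, descriptively only.

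This is a cheap improvement: analysis-plan wording and one derived variable, with no change to visits, treatment or sample size. The downside is one extra term in a recurrence model with few events, which is why the finer coding stays out of the model.
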